**Nitrous Oxide Analgesia for External Cephalic Version:
A Randomized Control Trial**

Study Protocol

Original Version 9/30/2016

NT# NCT03502915

Investigational Protocol

Study title: Randomized Controlled Trial of Nitrous Oxide Analgesia in External Cephalic Version (ECV)

Lead investigator: [name] MD

Co-investigators: [name] MD, [name]

Background and Purpose of the investigation:

Breech presentation occurs in 3% of pregnancies. The Term Breech Trial in 2000 demonstrated that planned cesarean delivery could reduce fetal morbidity and mortality compared to planned breech vaginal delivery¹. As a result of these findings the incidence of cesarean delivery for breech presentation increased. In the U.S., nearly 90% of breech deliveries are performed by cesarean delivery². It is recommended to offer external cephalic version (ECV), a maneuver to turn the fetus from breech to cephalic position, when possible to avoid cesarean delivery². Although ECV is typically a brief procedure, it is associated with a moderate amount of pain³. The associated pain discourages some women from pursuing ECV and limits the ability of the obstetrician to perform this maneuver.

There is evidence that success of ECV is increased and pain is decreased when the procedure is performed under neuraxial anesthesia^{4,5}. However, the use of neuraxial anesthesia for ECV remains controversial given the invasiveness of the procedure and associated risks. Risks may include maternal hypotension, post-dural puncture headache, urinary retention, pain at the injection site, meningitis, paresthesia, and weakness. In addition, post-procedure monitoring is required after a neuraxial anesthetic which may be considered excessive for this short procedure. At UNC, the standard of care is to offer no analgesia to the pregnant woman undergoing ECV.

Nitrous oxide is an ideal drug for use during ECV. Nitrous oxide provides analgesia, decreases the perception of pain, and has an anxiolytic effect. Some women find nitrous to be a satisfactory and effective agent for analgesia during labor⁶. It has a rapid onset and offset and is noninvasive. Pain during ECV is of relatively short duration, less than 5 minutes, and can easily be anticipated³. Nitrous oxide could be easily self-administered to treat the pain associated with ECV in much the same manner as it is commonly used to treat the pain associated with strong uterine contractions during labor. For these reasons, nitrous oxide may be an appropriate analgesic for patients undergoing ECV.

Worldwide, nitrous oxide is often used for labor analgesia and interest in nitrous oxide use continues to increase in the United States⁶. It has been estimated that nitrous oxide is used by approximately 50% to 75% of laboring women in the United Kingdom, and approximately 60% in Finland. Nitrous oxide is used and widely considered to be safe in many parts of the world including Canada, Australia, and New Zealand⁷. Use in the United States is currently estimated

to be <1% but with rapidly increasing interest. UNC is the third academic institution in the U.S. to offer self-administered inhaled nitrous oxide for labor analgesia.

In the context of obstetric analgesia, “nitrous oxide” refers to a half-and-half combination of oxygen and nitrous oxide gas, called by the trade name “Nitronox” (in the United States) and “Entonox” (in the United Kingdom). It is self-administered by the laboring woman using a face mask. It is generally administered beginning approximately 30 seconds before the onset of a strong contraction until the pain associated with contraction eases⁷. The Nitronox delivery system includes a demand valve which limits delivery of nitrous oxide to the inspiratory phase of ventilation. It also includes a scavenging system that collects expired gasses to minimize environmental exposure.

Nitrous oxide is the only commonly used inhaled labor analgesic in modern obstetric practice and has a long history of safe use. This is likely related to the ease of administration, lack of flammability, absence of pungent odor, minimal toxicity, minimal depression of the cardiovascular system, lack of effect on uterine contractility, and the fact that it does not trigger malignant hyperthermia⁷.

In a systematic review of available literature in 2014, Likis notes that the most common maternal adverse effects are unpleasant side effects that affect tolerability (e.g., nausea, vomiting, dizziness, and drowsiness). Some of the above listed maternal adverse effects are common in laboring women regardless of whether analgesia is used⁶. We believe administration of nitrous oxide for ECV to be a safe practice with a favorable risk to benefit ratio. Confidence in the safety of this study is bolstered by the long history of safe administration to women in labor.

There are concerns of potential neurotoxicity of nitrous oxide, but this finding is limited to animal studies and only when used in combination with other anesthetics. Nitrous oxide is transmitted via the placenta and is rapidly eliminated by the neonate after birth once breathing begins. No evidence exists to suggest altered neonatal outcomes associated with the use of nitrous oxide alone. Apgar scores in newborns whose mothers used nitrous oxide did not differ significantly from those of newborns whose mothers used other labor pain management methods or no analgesia⁶.

Recently published literature has provided evidence that exposure of the immature animal brain to anesthetics during the period of rapid synaptogenesis triggers rapid neurodegeneration and causes significant long-term cognitive impairment⁸. However, nitrous oxide, by itself at subanesthetic concentrations, triggers little or no neuroapoptosis in the infant rat brain⁹. In our study, nitrous oxide will be delivered at 50%, which is an analgesic or subanesthetic concentration. In addition, no other analgesic or anesthetic agents will be administered in combination with nitrous oxide.

Nitrous oxide is classified as a Class C drug in pregnancy by the US FDA, “Risk cannot be ruled out. Either studies in animals have revealed adverse effects on the fetus (teratogenic or

embryocidal effects or other) and there are no controlled studies in women, or studies in women and animals are not available. Drugs should be given only if the potential benefits justify the potential risk to the fetus." As discussed above, concerns about nitrous oxide induced neuroapoptosis are not applicable to this study. Nitrous oxide has been used safely in pregnancy for greater than 100 years, and many commonly used and widely accepted drugs are used for analgesia and anesthesia in the parturient that are also considered Class C. The class C rating of nitrous oxide is likely due to the absence of large randomized controlled studies in women.

As an example of a comparable Class C analgesic option in labor, other than an epidural, remifentanil has also been widely used and studied. In a meta-analysis of RCTs studying remifentanil for labor analgesia, remifentanil patient controlled analgesia was found to be safe and effective when compared with other analgesic options in labor¹⁰. In addition, remifentanil has been used and studied in the setting of ECV where it was found to reduce pain and increase patient satisfaction¹¹. We do not routinely offer remifentanil for ECV at UNC Hospitals, but hope to show similar analgesic results with nitrous oxide.

The potential benefits of this study include increased patient satisfaction, decreased pain, increased success of ECV, and decreased cesarean section rate. In addition, after completion of this study, nitrous oxide analgesia may become more routinely used for ECV as well as other painful procedures such as epidural placement, peripheral intravenous access, arterial access, obstetric examinations etc. If effective, this study could also help other health care providers with the decision to use nitrous oxide for analgesia outside of the obstetric population in the future.

Study Design

Double blind randomized controlled trial

Subject Selection

Participants: Pregnant women with breech presentation at 37 weeks EGA who are scheduled to undergo external cephalic version.

Subjects eligible for study entry:

1. Female 18yo or greater
2. Scheduled to undergo ECV due to singleton breech presentation
3. Not scheduled to have spinal or epidural anesthesia during the ECV procedure
4. American Society of Anesthesiology (ASA) Physical Status 1, 2 or 3.
5. Able to provide informed consent and adhere to study protocol

A subject will not be eligible for the study if he/she meets any of the following criteria:

1. Current or historical evidence of any clinically significant disease or condition, especially cardiovascular or neurological conditions that, in the opinion of the Investigator, may

- increase the risk of exposure to nitrous oxide or complicate the subject's postprocedural course.
- 2. Significant medical conditions or laboratory results that, in the opinion of the Investigator, indicate an increased vulnerability to study drugs and procedures.

Study Procedures:

Potential subjects will be identified as they are scheduled to undergo ECV at the UNC Department of Obstetrics and Gynecology. Subjects will be enrolled in the study by one of the study investigators. Details of the study will be reviewed with potential subjects and those wishing to enroll in the study will be consented for the study by one of the study investigators. Once enrolled participants will be randomized to receive either a mixture of 50% nitrous oxide in 50% oxygen or 100% oxygen, both of which will be delivered via the Nitronox apparatus. Demographic variables will be recorded for each participant at the time they are enrolled in the study (weight, BMI, age, ethnicity, gestational age, parity, placentation, breech position, hx of previous cesarean delivery, hx of previous ECV)

The Nitronox apparatus will be set up to deliver either 50% nitrous oxide in 50% oxygen or 100% oxygen by an anesthesia provider covering labor and delivery who is not involved in the study. The Nitronox device will be covered to prevent participants, study investigators and obstetricians performing the procedure from knowing whether nitrous oxide is being delivered. Nitrous oxide is odorless and colorless, so in that way is indistinguishable from oxygen.

Participants will be prepared for ECV according to current protocols for ECV at UNC. IV access will be obtained and tocolytic agents will be given according to current practice and protocols. Monitoring of maternal and fetal vital signs will be done according to current protocols.

Immediately before an ECV attempt participants will breathe through the facemask of the Nitronox device for 30 seconds and will then be free to use the device ad lib during the ECV attempt. Immediately following each attempt, while fetal monitoring is occurring, the participants will be asked to rate their maximum pain score (0-10) during the previous attempt. They will also be asked to rate their current level of anxiety (0-10). This process will be repeated for any further ECV attempts.

At conclusion of all ECV attempts, while fetal monitoring is occurring, the participants will be asked to rate their current level of pain (0-10), their satisfaction with the procedure (0-10) and about any side effects they experienced (nausea, vomiting, dizziness, headache, other). Participants will continue to be monitored on labor and delivery as current protocol dictates, typically 30 minutes of maternal and fetal monitoring if there are no complications and fetal status is reassuring.

Following the procedure, the obstetrician who performed the procedure will be asked to rate how difficult they felt it was to perform the procedure (1-10) and to rate how much they felt the analgesic provided assisted in performing the procedure (1-10). They will also be asked to

indicate whether they thought the patient was in the treatment or placebo arm of the study. This will be recorded to address the adequacy of blinding.

Outcomes that will be recorded following the procedure include whether the procedure was successful, the number of attempts performed, complications associated with the procedure (maternal hypotension, fetal bradycardia transient/persistent, emergent cesarean delivery, cord prolapse, placental abruption, other), eventual mode of delivery, indication for cesarean delivery if performed and analgesic/anesthetic used for delivery if any.

All study variables will be assessed and recorded by one of the study investigators to ensure consistency in data collection.

Study outcome evaluation:

A suite of preliminary tabular and graphical investigations will be conducted prior to quantitative analyses to provide a thorough understanding of the data. These investigations will include:

- a. Descriptive statistics, with histograms and boxplots on continuous variables
- b. Frequency distributions on discrete variables
- c. Correlations among potential model predictors and covariates to reveal potential variable multicollinearity problems.

In addition to the information compiled from the preliminary investigations described above, Chi-square tests of association for the outcome variables of interest and principle predictors will be conducted to reveal important relationships and justifications for more robust analyses.

The primary outcome of the study is pain experienced during ECV. The null hypothesis of this outcome is that there is no difference in pain scores between patients who use a mixture of 50% nitrous oxide and 50% oxygen during ECV (treatment group) compared to those that use oxygen only during ECV (placebo group). Pain scores during each ECV attempt will be recorded for each participant. For those participants who have more than one attempt these scores will be averaged to obtain a single score for the entire procedure. A student t-test will then be performed to evaluate the null hypothesis of no difference in pain scores between the treatment vs placebo groups. A difference in pain score of 2 (Scale: 0-10) is considered clinically significant. Based on a mean pain score difference of 2 and an average standard deviation of 2.5 for the treatment and placebo groups, a statistical power of 80% is expected. Consideration will be given to categorizing the patients into “Low”, “Moderate” and “Severe” pain score categories along clinical guidelines to further assess the impact of analgesia on pain severity. Where feasible, both p-values and confidence intervals for odds ratios from logistic regression and/or parameter estimates from general linear modeling will be reported.

Secondary outcomes of the study include patient anxiety experienced during the ECV procedure, pain scores following the ECV procedure, patient satisfaction with ECV procedure, side effects experienced and OB providers ratings of ease of procedure.

We will be recording whether the ECV procedures are successful and whether any complications occur as a result of the ECV procedure, but given that our study is powered to evaluate patient pain and not these outcomes we do not expect to see any differences. Previous studies have shown that analgesia alone does not alter success rates of ECV, this includes a previous study that used nitrous oxide during ECV.

Complications of ECV are very rare. Given that nitrous oxide has been demonstrated to be safe for labor analgesia, a similar patient population to ours, we do not anticipate that we would be able to detect any differences in complications in this patient population. These variables are being recorded for completeness.

Several variables known to influence the effectiveness of ECV (BMI, age, ethnicity, gestational age, parity, placentation, type of breech position, amniotic fluid level, tocolytic used, history of prior c-section) are being recorded for each participant. We are also recording whether participants have previously undergone ECV with a prior pregnancy since this could influence their expectations of this procedure. These variables will be analyzed using chi-square or fisher exact test to ensure that there are no differences in these variables between the treatment and placebo groups.

Either a general linear model or a logistic model will be employed to assess the effect of the main effects, interactions, and appropriate covariates on the primary outcomes of interest. Selected covariates and potential confounders will be included in a “forward” regression model and subsequently retained in the final model only if found to explain a significant amount of the variability in the outcome. Candidate covariates include patient anxiety during the ECV procedure, patient satisfaction, ECV success and history of previous ECV.

All data will be recorded during one interaction with the participants and will not require participants to be contacted following the ECV procedure. Because of this the likelihood of missing data and drop out is extremely low.

The only area where we might expect to have missing data is for delivery information and type of anesthetic used for delivery since not all patients who have an ECV at UNC actually deliver at UNC. However, this data is included on the data sheet only because we are curious to know whether involvement in the study might influence participants to try nitrous oxide for labor analgesia. The use of nitrous oxide for labor, while common worldwide, remains uncommon in the United States. Many women who present in labor have actually never heard of the use of nitrous oxide for labor analgesia. We also have parturients who come to UNC to deliver specifically because we offer nitrous oxide for labor analgesia. It would be interesting to know whether our contact with them through the consent process may inform them of and potentially lead them to consider use of nitrous oxide for labor analgesia.

Power analysis:

A power analysis to determine the sample size required to see a difference in pain score of 2 between the groups was performed which yielded the needed sample size of 50. This analysis

was based on pain scores from previous studies on pain during ECV in the setting of no analgesia as well as use of nitrous oxide or remifentanil for treatment of pain (Burgos et al, Fok et al, Munoz et al).

Normal Distribution $\alpha=0.05$	
Mean Difference	2
Standard Deviation	2.4
Total Sample Size	50
Number of Sides	2
Power	0.823

Lognormal Distribution $\alpha=0.05$	
Group 1 Geometric Mean	4.5
Group 2 Geometric Mean	6.5
Coefficient of Variation	0.45
Total Sample Size	50
Number of Sides	2
Power	0.843

Data handling:

At the time of enrollment in the study each participant will be assigned a unique study ID number. A spreadsheet that links the patient's study ID number with the patient's name and medical record number will be kept on a secure department server that only the investigators will have password protected access to. The remainder of study data will be coded and information regarding an individual patient will only be linked to their study ID number. Study ID numbers will be recorded on each data collection sheet. Data from the data collection sheets will then be entered into a database for analysis. In this way a coded hard copy of data for each participant will exist that does not include any patient names or medical record numbers, but will allow to ensure the integrity of the data within the database. All coded data will be entered into a Microsoft excel spreadsheet by one of the study investigators. This will be a password protected file to ensure that data cannot be manipulated by anyone other than the study investigators. Data analysis will be performed as described above by the study investigators with assistance from a consulting statistician as needed. The consulting statistician will not have access to any patient identifiable data, but would solely be working with the coded data.

References:

2. ACOG Committee Opinion No. 340. Mode of term singleton breech delivery. *Obstet Gynecol*. 2006;108(1):235-237.

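### The only anxiety item asks for the level felt at the moment of asking, after each attempt, so the rating after the last or only attempt may not capture the anxiety during ECV that the secondary outcome names.

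*Combined protocol and SAP*

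**What the plan says.** Study outcome evaluation defines the outcome: "Secondary outcomes of the study include patient anxiety experienced during the ECV procedure". The item meant to supply it is in Study Procedures. The time of asking is "Immediately following each attempt, while fetal monitoring is occurring", and two questions are put. For pain, "the participants will be asked to rate their maximum pain score (0-10) during the previous attempt". For anxiety: "They will also be asked to rate their current level of anxiety (0-10". Both are then asked again where needed: "This process will be repeated for any further ECV attempts". No other anxiety item appears in the documents, whether at baseline, during an attempt, or looking back over one.

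On the gas, the woman breathes through the mask for 30 seconds before an attempt and "will then be free to use the device ad lib during the ECV attempt". The Background says that nitrous oxide relieves anxiety and that it acts and wears off quickly.

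On combining ratings, the plan has a rule for pain: "For those participants who have more than one attempt these scores will be averaged to obtain a single score for the entire procedure". It has none for anxiety.

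The anxiety variable has a second use, in the regression model for the primary outcome: "Candidate covariates include patient anxiety during the ECV procedure, patient satisfaction, ECV success and history of previous ECV".

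**The concern.** The label refers to a period and the item refers to a moment after it. For a woman with a single attempt, that moment is her only anxiety rating. Two things could separate the rating from what she felt during the attempt. One is the rapid offset of a gas described as used only just before and during attempts. The other is her reaction to whether the fetus turned.

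If the arms differ little on this item, the investigators could not tell whether the gas failed to relieve anxiety during attempts or relieved it and had partly worn off by the time of asking. The reaction to the result is mainly noise if success is equal between arms, as Study outcome evaluation expects. If success differs, which the Background lists as a potential benefit, part of the difference in the last rating could reflect success rather than relief during the attempt.

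The use of the same variable as a covariate for pain is a separate problem. It exists however the item is worded.

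**Working it through.** The plan gives no figure for anxiety to reproduce, so the check sets its own items side by side.

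| Item (Study Procedures) | What is asked | When | Outcome it serves (Study outcome evaluation) |
|---|---|---|---|
| Pain, per attempt | highest level over the attempt just ended | after each attempt | primary: pain during ECV |
| Anxiety, per attempt | level at the time of asking | same step | secondary: anxiety during ECV |
| Pain, final | level at the time of asking | after all attempts, during monitoring | secondary: pain after ECV |

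The link in the third row is an inference: it is the only item that can supply that outcome.

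1. For pain, the plan separates the two periods by wording. Recall of the attempt gives pain during; the present level at the end gives pain after. For anxiety, present-level wording carries the label for the period during ECV.
2. A rating between two attempts can fairly be read as anxiety during the procedure, since the procedure is still going on. The doubt attaches to the rating after the last or only attempt. Every woman who has an attempt has exactly one of these.
3. To size the loss one would need the offset time of the gas, the delay before the question, the distribution of attempts and the expected effect on anxiety. The documents give none of these.
4. The Power analysis is built on pain scores alone, and the primary test is a t-test on averaged pain. Neither uses the anxiety item.

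Covariate use, as an illustration only. Let a be the effect of the gas on rated anxiety, in points, and b the within-arm slope of pain on anxiety. In a linear model, adjusting pain for anxiety leaves

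adjusted effect = total effect − a × b.

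The total effect is the plan's 2-point difference. The values of a (0.5 to 1.5) and b (0.3 to 0.5) are assumptions; the documents give neither.

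- Low end: 0.5 × 0.3 = 0.15, leaving 1.85 (7.5% removed).
- High end: 1.5 × 0.5 = 0.75, leaving 1.25 (37.5% removed).

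This range says nothing about the size of the wording problem. If the present-level item misses the effect on anxiety, a is small and little is removed. An item that captures the effect better would make a larger, so rewording does not cure the covariate problem and could increase it.

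**The case against.** The strongest reply is that the rating is taken at once, straight after free use of the gas, and is a near-contemporaneous proxy. The outcome label also speaks of the procedure rather than of attempts. Study Procedures speaks of the time after the procedure only once the monitoring paragraph is finished, so monitoring may count as part of it. On that reading the last rating is as much within the procedure as those between attempts. The comparison with final pain is not decisive either, because that item belongs to a separate step at the end.

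Much of this stands. It makes the last rating ambiguous rather than plainly off target. It does not remove the mismatch: the plan chose recall wording for pain in the same step, and nowhere says that present anxiety stands in for anxiety during the attempt.

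A reader might go further and infer that the item does not measure the outcome at all, or that a share 1/k of the score is lost for a woman with k attempts (all of it with one, half with two). The documents do not support either. The share borrows an averaging rule stated only for pain, and it treats an immediate rating as carrying no information about the attempt just ended.

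It is also fair to say that recalled anxiety is asked at the same moment and can be coloured by success or failure too. The data collection sheet is not among the documents, so its wording cannot be checked.

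**Conclusion.** The point holds as a mismatch between an outcome label and its item. The rating after the last or only attempt may not capture anxiety during that attempt, and a small or null result would be ambiguous. No loss is shown and none can be sized from the documents. The finding concerns one secondary outcome; the primary t-test and the sample size stand.

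The missing rule for combining anxiety ratings over attempts is a further, smaller gap.

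The covariate point also holds, independently of the wording. The plan expects the gas to affect anxiety, so adjusting pain for anxiety rated after treatment can remove part of the treatment effect. A reader might infer that the main result is at risk. That does not follow: the primary analysis is the unadjusted t-test, and anxiety is only a candidate in a forward-selected model. The range of 0.15 to 0.75 points rests wholly on assumed inputs.

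**What to change.** - **Reword the item.** After the pain question, so that the primary outcome is not influenced, ask for the highest anxiety (0-10) in the attempt just finished. State that these ratings are averaged over attempts as for pain. This costs one line on the data sheet and one sentence in the plan. The downsides are brief recall, already accepted for pain, and possible colouring by the pain answer just given and by the success or failure of the attempt. Peak anxiety is also a narrower quantity than anxiety in general.
- **Or relabel.** If the present-level item is kept, rename the variable as anxiety immediately after each attempt, both in the list of secondary outcomes and in the list of candidate covariates, and state how ratings are combined. This costs nothing but leaves anxiety during attempts without a direct measure.
- **In either case, drop anxiety rated after treatment from the candidate covariates for the pain model.** This removes one name from a list. If adjustment for anxiety is wanted, one 0-10 rating before the mask is first used would serve. It is an optional extra that fits the single interaction the plan describes, and it is not needed to resolve the mismatch.

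### No anxiety rating is planned before the study gas, so the secondary anxiety comparison cannot be adjusted for starting anxiety and the pain model has only a post-treatment anxiety covariate; the cost is precision, not bias.

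*Combined protocol and SAP*

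**What the plan says.** Under Study Procedures, the variables recorded at enrolment are listed as "weight, BMI, age, ethnicity, gestational age, parity, placentation, breech position, hx of previous cesarean delivery, hx of previous ECV". No anxiety or pain rating is among them. The same section has the woman breathe through the mask for 30 seconds just before an attempt and then use it as she wishes. After each attempt she rates her worst pain during it, and "They will also be asked to rate their current level of anxiety (0-10" is the accompanying instruction on anxiety. Current pain is asked once, after the last attempt.

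Under Study outcome evaluation, the plan states: "Secondary outcomes of the study include patient anxiety experienced during the ECV procedure, pain scores following the ECV procedure". The list continues with satisfaction, side effects and the obstetrician's ratings. No test, power figure or SD is given for anxiety. The covariate model in that section is aimed at the primary outcome. Its four candidate covariates are anxiety during the version, satisfaction, success of the version, and previous version.

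**The concern.** The Background section credits nitrous oxide with an anxiolytic effect, and anxiety is one of the outcomes that could show it. Women are likely to arrive with differing levels of anxiety. Without a rating taken before the gas, that spread stays in the error term of a comparison of about 25 against 25.

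The gap also reaches the primary outcome. The plan lists anxiety as a candidate covariate for pain, but the only anxiety rating it will hold is made after the gas and after the attempt. If the gas lowers anxiety, adjusting pain for that rating can remove part of the treatment effect. A pre-gas rating would not have this defect, and it cannot be collected later.

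**Working it through.** **Timeline.** Enrolment: demographic and obstetric variables only. Then the mask for 30 seconds, the first attempt, and only then the first pain and anxiety ratings. No rating described in the procedures precedes treatment, and the anxiety rating after attempt 1 is no substitute because it is already exposed to the gas.

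**Inputs from the documents.** Total N 50, two-sided alpha 0.05, and SD 2.4 in the power table (Power analysis). The Study outcome evaluation text says "A difference in pain score of 2 (Scale: 0-10) is considered clinically significant" and gives "an average standard deviation of 2.5 for the treatment and placebo groups, a statistical power of 80% is expected".

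**Assumptions.** 25 per arm (the allocation ratio is not stated). The SD for anxiety is not given, so the SD for pain during the version stands in, at 2.5 and at 2.4. The correlation r between pre-gas and later anxiety is not given and is varied.

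**Reproducing the plan's figure.** SE = SD × √(2/25).
- SD 2.4: SE = 0.679 and noncentrality 2/0.679 = 2.95. With 48 df the noncentral t gives power 0.823, as stated.
- SD 2.5: SE = 0.707 and noncentrality 2/0.707 = 2.83, giving power 0.791, consistent with the text's 80%.

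Both concern pain during the version. Nothing below changes them.

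**Effect of adjusting anxiety for a pre-gas rating.** One covariate multiplies the variance of the arm difference by

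(1 − r²) × (1 + 1/(N − 4)) = (1 − r²) × (1 + 1/46).

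The second factor charges for chance imbalance in the covariate. Degrees of freedom fall from 48 to 47. The difference detectable with 80% power is about 2.86 × SE at either df (unadjusted at SD 2.5: 2.86 × 0.707 = 2.02). The equivalent unadjusted N is 50 divided by the variance factor.

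| r | Variance factor | SE (SD 2.5) | Detectable difference, SD 2.5 | Detectable difference, SD 2.4 | Equivalent unadjusted N |
|---|---|---|---|---|---|
| unadjusted | 1 | 0.707 | 2.02 | 1.94 | 50 |
| 0 | 1.022 | 0.715 | 2.05 | 1.96 | 49 |
| 0.1 | 1.012 | 0.711 | 2.03 | 1.95 | 49 |
| 0.3 | 0.930 | 0.682 | 1.95 | 1.87 | 54 |
| 0.4 | 0.858 | 0.655 | 1.87 | 1.80 | 58 |
| 0.5 | 0.766 | 0.619 | 1.77 | 1.70 | 65 |
| 0.6 | 0.654 | 0.572 | 1.64 | 1.57 | 76 |

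**Break-even.** The variance factor equals 1 when r² = 1 − 46/47 = 1/47, so r = 0.146, or about 0.15.

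**Worst case.** At r = 0 the SE rises by √1.022 − 1, about 1%.

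**The case against.** The strongest reply is that nothing in the plan is wrong. Anxiety is a secondary outcome with no power claim, the primary power of 0.823 is untouched, and a baseline rating is an optional gain in efficiency whose size rests on a correlation the documents do not supply and an SD taken from another outcome. At r = 0.1 there is no gain. All of this stands and limits the point to a modest improvement.

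The absence is also inferred. The enrolment list is not exhaustive: amniotic fluid level and tocolytic are said elsewhere to be recorded but are not in it. The data sheet is not in the documents. The finding therefore rests on the procedures text, which sets out the timing of the other ratings in detail and mentions none before the mask.

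Three stronger readings are tempting, and the documents do not support them.

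- A reader might infer that an arm difference in anxiety could not be told apart from one the women brought with them. Allocation is randomized, so the unadjusted comparison is unbiased and its standard error already allows for chance differences at the start.
- A reader might infer the same loss for post-procedure pain. Women come for a scheduled procedure, and the Background describes the pain as lasting under 5 minutes. Pain before the gas may sit near 0 with little to adjust for. That is a judgement, but no figure in the documents points the other way.
- A reader might infer that the plan has no untreated covariate at all for the pain score. Previous version is a candidate covariate and is recorded at enrolment. What is missing is an untreated measure of anxiety.

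**Conclusion.** The point holds for anxiety, as a possible loss of precision. No pre-gas anxiety rating is described, so the anxiety comparison cannot be adjusted for starting anxiety, and any anxiety covariate in the pain model would be post-treatment. Under the stated assumptions, adjustment changes the SE by between a 1% increase (r = 0) and a 19% reduction (r = 0.6: 1 − √0.654). Above r of about 0.15 there is a gain. A worthwhile r is plausible for two ratings of the same feeling by the same woman, but the documents do not show it. A different anxiety SD would scale the detectable differences in proportion and leave the variance factors and break-even unchanged. No benefit to the primary pain comparison can be put in figures, because no correlation between anxiety and pain is given.

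**What to change.** In Study Procedures, before the mask is first applied, add one question: current anxiety on the same 0-10 scale. In Study outcome evaluation, state that anxiety is compared between arms with a linear model adjusted for that rating; without this sentence the question would be wasted. If anxiety is kept as a candidate covariate for the primary pain score, replace the rating made during the version with the pre-gas one.

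The cost is one short spoken question, one box on the data sheet and one degree of freedom. The plan already collects its ratings in a single interaction and has an investigator record them, so no visit, staff or procedure is added. If r proves near 0, the loss is about 1% of the SE. A matching pre-gas pain question may be added but is optional, since its gain for post-procedure pain is uncertain and may be nil. The change must be in place before women are treated, because the rating cannot be recovered afterwards.
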